# Summary

Protocol Title	The impact of Cranberries On the Microbiome and Brain in healthy Ageing sTudy (COMBAT): a feasibility intervention			
Protocol Number	Version 4.0, 7 th May 2019			
Sponsor	The University of East Anglia, Norwich, United Kingdom			
Primary Contact	[name] [contact]			
Chief Investigator	[name] [contact]			
Study Personnel	[name] [contact]			
	[name] [contact]			
	[name] [name] [contact]			
	[name] [contact]			
	[name] [contact]			
	[name] [contact]			
	[name] [contact]			
	[name] [contact]			
	[name] [contact]			
	[name] [contact]			
	[name] [contact]			
	[name] [contact]			

	[name]
	[name] [contact]
	[name]
	[contact]
	[name]
	[name] [name]
	[contact]
Study Site/s	Bob Champion Research and Education Building
	Norwich Research Park
	[name]
	[name]
	United Kingdom
	Norwich Clinical Research Facility (CRF)
	Quadram Institute Building
	Norwich Research Park
	[name]
	[name]
	United Kingdom
	Quadram Institute Building
	Norwich Research Park
	[name]
	[name]
	United Kingdom
	Norfolk and Norwich University Hospital (NNUH)
	[name]
	[name]
	United Kingdom
	Norwich Biorepository
	Bob Champion Research and Education Building
	Norwich Research Park
	[name]
	[name]
	United Kingdom
	Imperial College London
	South Kensington
	[name]
	United Kingdom
	University of Parma
	[name]
	[name]
	Italy

Objectives	
 
i) Investigate the impact of cranberry intervention on gut microbiome composition and metabolism after a 12-week intervention.
 
ii) Investigate the role of microbiome modulation and metabolism in mediating the effect of the cranberry intervention on cognition and brain physiology (MRI)
 

Outcomes	
 
Gastrointestinal microbiota analysis
 
Cognitive function
 
Neuroimaging: MRI
 
Biochemical assessment: to include flavonoid metabolites
 

Design	Single-centre randomised, double-blind, placebo-controlled parallel intervention trial.
Participants	60 healthy adults (i.e. n=30 in treatment and control groups) aged 50 to 80 years.
Product to be Tested	Cranberry Institute freeze-dried cranberry powder estimated to contain 500mg plant-derived polyphenols per day.
Treatment Details	Twice-daily oral consumption of freeze-dried cranberry powder or matched placebo powder for 12 weeks.

# 2. Abbreviations

ACE-III	Addenbrooke's Cognitive Examination III
BDNF	Brain-Derived Neurotrophic Factor
BOLD	Blood-Oxygen-Level Dependent imaging
BPQ	Body Perception Questionnaire
СВІ	Cambridge Behavioural Inventory
CCI	Cognitive Change Index
CRF	Clinical Research Facility
ELISA	Enzyme-Linked Immunosorbent Assay
FDR	False Discovery Rate
GAD7	Generalised Anxiety Disorder questionnaire 7
GCP	Good Clinical Practice
IPAQ	International Physical Activity Questionnaire
KSS	Karolinska Sleepiness Scale
MRI	Magnetic Resonance Imaging
MS	Mass Spectrometry
NNUH	Norfolk and Norwich University Hospitals
PHQ-9	Patient Health Questionnaire 9
PI	Principal Investigator
PIS	Participant Information Sheet
PSQI	Pittsburgh Sleep Quality Index
RCFT	Rey Complex Figure Test
SCFA	Short Chain Fatty Acid
тмт	Trail Making Test
UEA	University of East Anglia

# 3. Background

The human microbiome has recently emerged as a significant contributor to nutrition, health and incipient disease development. This microbial impact is, however, not limited to the gut, instead the human microbiome interconnects the gastrointestinal tract with the central nervous system via a complex series of highly interactive and symbiotic host-microbiome signalling systems (Bhattacharjee & Lukiw, 2013). In particular, gut bacteria may contribute to brain function through the cumulative effects of microbial metabolites (Cryan & Dinan, 2012), such as bile acids, choline and short-chain fatty acids (SCFAs) that are essential for health (Nicholson et al., 2012). Microbiome composition is relatively stable throughout adulthood, though changes in dietary composition and diversity are considered the main drivers of the shifts in microbiome structure and activity (Claesson et al., 2012). Such findings argue in favour of an approach of modulating the microbiome and indirectly brain functions with dietary interventions containing defined nutrients and food bioactives designed to promote healthier ageing. Amongst those nutrients, polyphenols have been consistently reported to play a protective role against cognitive decline (Vauzour, 2014) and have the ability to modify the microbiome composition and metabolism (Tuohy, Conterno, Gasperotti, & Viola, 2012). However, although it has become increasingly clear that the metabolic activities of the gut microbiome provide a mechanistic connection between environmental factors and brain functions (Hsiao et al., 2013), there have been no previous studies examining gut bacterial composition and metabolism in older adults following Cranberry intake and their impact on cognitive functions. Such a Cranberry-mediated cognitive resilience would be highly relevant for the increasing ageing population, for whom signs of cognitive decline are often the harbinger of an incipient dementia. More specifically, ageing related cognitive deficits are usually starting after the age of 65 when the incidence of dementia rises as well. In particular, medial temporal lobe brain regions are highly sensitive to ageing effects, resulting in subtle memory and navigation problems, which are mediated via these brain regions. The proposed project tries to rectify the shortcoming in our knowledge of how Cranberries impact on gut-brain axis and therefore cognition. Success in this project would have important implications for an ageing population where an increase in healthy ageing is greatly desired. As such, it is predicted to considerably advance the scientific knowledge based in the area and to establish whether the microbiome is an important therapeutic target when designing intervention and novel foods that aim to improve cognition. The potential benefits in terms of quality of life are relevant to the population as a whole, as are the potential savings in health care costs. It is estimated that the total annual cost of dementia will escalate to 1.7 trillion euros by 2030. In addition to the general consumer and in particular the elderly, the data resulting from this proposal will also inform future pharmacological and non-pharmacological interventions in the prevention of dementia with the gut-brain axis as its main target.

# 4. Trial Objectives

We propose for the project to:

i) Investigate the impact of a cranberry intervention on gut microbiome composition and metabolism after a 12-week intervention.

ii) Investigate the role of microbiome modulation and metabolism in mediating the effect of a cranberry intervention on cognition and brain physiology.

# 5. Trial Design

The study will be a single-centre, 12-week, double-blind, placebo-controlled parallel intervention to investigate the impact of cranberry on the gut microbiome, cognition, and brain physiology. All participants will attend three study visits: one screening visit, one baseline visit at the beginning of the 12-week intervention, and one post-intervention follow-up visit.

# 6. Participants

This study will include 60 (i.e. n=30 control and treatment groups) healthy older adults. Volunteers aged 50-80 years old with no memory complaints will be recruited. Married couples who live together will be particularly targeted to reduce the variability in background diet patterns.

#### 6.1 Recruitment

Participants will be identified through existing studies being conducted at UEA where participants have agreed to be contacted about relevant studies, community- based advertising (e.g. recruitment posters, leaflets, talks) and local participant databases. We will also be using 'Join dementia research' (JDR) as a recruitment tool. This is an on-line self-registration service that enables volunteers with memory problems or dementia, carers of those with memory problems or dementia, and healthy volunteers to register their interest in taking part in research. The purpose of JDR is to allow such volunteers to be identified by researchers as potentially eligible for their studies. Researchers can then contact volunteers, in line with the volunteers preferred method of contact, to further discuss potential inclusion. JDR is funded by Department of Health working in partnership with the charities Alzheimer's Society and Alzheimer's Research UK and is Health Research Authority (HRA) endorsed. The on-line service and all associated documentation, methods of contacting volunteers and handling of data, were reviewed by a specially convened HRA committee which included experts in research ethics, data protection and information governance. Formal endorsement was issued by the HRA in a letter dated 20 May 2014. The study has also been adopted by the NIHR Clinical Research Network Portfolio database, which can also assist with recruitment of research participants as it allows access to wider recruitment databases.

## 6.2 Inclusion Criteria

Participants are included in the study if they have all of the following:

• Aged between 50 and 80 years old.

- Male and female.
- Are generally fit and healthy.
- Willing and able to provide written informed consent.
- Fluent in written and spoken English.
- Normal or corrected to normal vision and hearing.
- Understands and is willing and able to comply with all study procedures.

The age range of 50 to 80 year is critical as cognitive deficits can commence in people in their 50s when people do not show yet significant structural brain changes, which typically occur with more advanced age (>80 years). Hence any dietary intervention needs to target people at early yet increased risk (>50) but with brain correlates still intact (<80) as to improve brain and cognitive functioning.

#### 6.3 Exclusion Criteria

Participants will be excluded from the study if they have any of the following:

- Diagnosis of any form of dementia or significant neurological condition.
- Significant memory complaints.
- History or MRI evidence of brain damage, including significant trauma, stroke, learning difficulties or serious neurological disorder, including a loss of consciousness for more than 24 hours.
- Currently smoking or ceased smoking less than 6 months ago.
- Chronic fatigue syndrome, liver disease, diabetes mellitus, or gall bladder abnormalities.
- History of alcohol or drug dependency.
- Clinically diagnosed psychiatric disorder.
- Existing diagnosed gastrointestinal disorder.
- Known allergy to the intervention supplement.
- Any significant medical condition likely to affect participation.
- Currently a participant or have been a participant in any other study involving an investigational product within the last 4 weeks.
- •
- Major cardiovascular event, such as myocardial infarction, within the last 12 months.
- A current diagnosis of cancer, or treatment for cancer that has concluded less than 12 months prior.

Participants will be eligible for the study if they are on blood pressure lowering medication only if the dose has been stable for 2 months.

Participants will not be eligible for the study if they are currently prescribed anticoagulant medicine such as warfarin.

Regarding supplements and diet, participants will not be eligible if they take and/or unwilling to stop taking the following:

- Flavonoid containing supplements (and unwilling to cease intake during, and 1 month preceding the trial) or unwilling to maintain existing intake of other supplements.
- High flavonoid intake defined as > 15 portions of flavonoid rich foods per day.
- Any other supplements that could have a significant impact on the outcome measures.

Participants will not be eligible to undergo the neuroimaging component of the study if they have any of the following:

- Cardiac pacemaker
- Claustrophobia

To ensure safety within the MRI scanner, access to medical records or further inquiry will be required if participants indicate that they may have had any of the following:

- Heart surgery
- Brain, head, spine or eye surgery
- Aneurysm clips
- Hydrocephalus shunt
- Metal dust or fragments in the eye
- Metal injuries (eg. shrapnel, bullets, pellets)
- Electronic, mechanical, or magnetic implants
- Operations involving metal implants, plates, clips, stents, bands or expanders
- Operations within the previous 8 weeks
- Kidney problems
- Have had liver transplant or waiting for a liver transport
- Fits, blackouts, or epilepsy
- Piercings, hearing aids, dentures (to check if they are removable)
- Medication patches, tattoos, permanent eyeliner or makeup

For female participants:

- Chance of pregnancy
- Breast-feeding
- Intrauterine contraceptive device (IUD)

For cases of operations, implants, or devices a surgeon's report will be requested from the participant's medical records, which will then be reviewed by the radiologist at NNUH before proceeding with the MRI scan.

If participants are unable or unwilling to undergo an MRI scan, they are still able to participate in other components of the study.

#### 6.4 Contact with Potential Participants

The initial approach to potential participants who have expressed interest in research participation provides the opportunity for information to be provided and to ask questions about the study before informed consent is obtained. Where participants have provided consent to be contacted regarding this study, written information (i.e. PIS and an invitation letter) will be provided to the participant. Potential participants who are identified from the pre-existing databases will first be phoned to be

screened for study eligibility and verbally provided with information about the study procedures. Potential participants will then be mailed the written information if they have not already received this. After sending the PIS and invitation letter, potential participants will be again contacted at least one week later, giving them sufficient time to read the information, consider their participation, and consult with others. Following verbal consent to participate, when they come to their first trial visit at a mutually agreed date and time, the researcher will go through the study verbally and with written information and give further opportunity for any questions to be answered. Participants are then asked to sign a consent form of which the contents are outlined under the section 12.3 Consent.

#### 6.5 Withdrawal of Participants

Participants may be withdrawn from the study for the following reasons:

- At their own request
- If continuation of the study would be detrimental to their wellbeing
- Adverse Event (AE) or Serious Adverse Event (SAE)
- Non-compliance
- Loss of mental capacity of consent

As soon as the research team became aware that a participant had lost the capacity to consent or has met one of the exclusion criteria, then that participant would be fully withdrawn from the study such that no further samples nor cognitive assessment data would be collected. As we are targeting healthy volunteers with no diagnosis of dementia or neurological condition, the loss of capacity during the study is extremely unlikely.

If a participant is prematurely withdrawn from the study for any reason after product administration, the investigator must make every effort to perform these Follow-Up Visit assessments: Review of concomitant medications, and review adverse events. This information should be recorded in the case report form. In all cases, the reason for withdrawal must be recorded in the case report form.

#### 6.6 Reimbursement

Participants will be financially reimbursed £25 for participation in this study. Attendance at all research visits will be required in order to receive the full amount, and this is agreed to on the participant consent forms.

Additionally, should any forms or questionnaires need to be posted to the research team, the participants will be supplied with reply paid envelopes which will cover the cost of postage.

# 7. Intervention

All participants will attend for three clinical visits: one screening visit, one baseline visit and one follow-up visit after the 12-week intervention.

#### 7.1 Pre-Treatment Screening

At the first contact with potential participants, individuals will be screened over the telephone according to the inclusion and exclusion criteria listed above. Participants will also provide verbal consent to continue with the study over the phone before written consent is obtained at the first screening visit.

Participants will be invited for a screening visit at the Clinical Research Facility prior to the treatment phase of the study. During this first screening visit participants will provide informed consent to the study and will undergo screening measures for cognition and indications of health, including blood pressure.

All participants will be screened via cognitive screening tests (ACE-III score > 88/100), as well as general physical health (normal blood pressure & haemoglobin levels, no psychiatric or alcohol history).

Screening of plasma biochemistry

A fasted blood sample will be taken at the screening assessment visit, using a standard gauge needle and vacutainer system; 22mL (10mL in SST tube, 8mL in CPT tube and 4ml in EDTA tube) and sent to the accredited pathology laboratories for determination of markers of general health.

The following will be measured by the accredited pathology laboratories, following standardised procedures:

- Full blood count analysis (white cell count (lymphocytes, neutrophils, monocytes, eosinophils, basophils), red cell count, haemoglobin, haematocrit, mean corpuscular volume (MCV), mean corpuscular haemoglobin (MCH), platelet count).
- Urea and electrolytes (sodium, potassium, bicarbonate, urea and creatinine).
- Liver function (total bilirubin, total protein, albumin, globulin, alkaline phosphatase (ALP), alanine aminotransferase (ALT), gamma glutamyl transferase (GGT)).

#### Urinalysis

The midstream spot urine sample collected at the clinical screen will be tested to assess pH, the presence of protein, glucose, ketones and blood, as indicators of general health (using a Combur 9 Test®, Roche Diagnostics Ltd., or similar dipstick method).

#### 7.2 Treatment Period

#### Treatment to be Administered

After screening and enrolment, each dyad will be assigned to the intervention (CI freeze-dried whole cranberry powder) or the control group (CI Placebo powder, matched for appearance and taste to the cranberry powder) using a randomisation algorithm. It is proposed that the active group will be supplemented with 500mg total polyphenols per day, consisting of 280 mg/d proanthocyanidins, 81 mg/d flavonols and 54 mg/d anthocyanins. This dose has been selected to be physiologically relevant and shown previously to independently impact on systemic vascular function and cognitive performance (Neshatdoust et al., 2016; Rodriguez-Mateos et al., 2016). The control intervention will be matched for energy and macronutrients content.

This intervention will be provided in the form of a freeze-dried powder which can be incorporated into beverages and food with the daily dose spread over two servings in order to maximize the physiological impact (based on our current understanding of bioavailability). Participants will be advised not to alter their usual calorie intake, asked to document any unusual symptoms or side effects and to keep a diary of illness and medication. Habitual dietary intake will be assessed using a validated, semi-quantitative, food frequency questionnaire (FFQ) based upon the SLAN study (Harrington et al., 2011).

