#### Assigning Subjects to Treatment Groups

To minimise bias this study will employ both randomisation and blinding. Eligible, recruited participants will be assigned a participant number. The participant will receive the treatment that has been randomly allocated to that participant number.

Randomization codes will be kept in a sealed envelope in a secure filing cabinet. While the study is a double blind trial, study investigators will know the location of, and have access to, the sealed randomisation code envelope. This is in the event of an emergency where the content of the treatment is needed to be known. In the event that the code break envelope is opened, the ethics committee will be informed. Each participant's un-blinding would be considered on a case-by-case basis following authorisation by the Safety Committee which includes the study research nurses, the chief investigator ([name]) and advice from study members responsibly for medical oversight.

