# 10. Data Analysis

Statistical Analyses

For each outcome measure, data will be manually screened and (only) data deemed 'invalid' will be omitted from analyses. Data will be deemed invalid if a biological rational sustains this assumption, e.g. non physiological values. These invalid data and the reason for exclusion will be reported in the final report.

Parametric statistical analyses will be performed, except where normality cannot be achieved, in which case equivalent non-parametric analyses will be performed.

Demographic, behavioural and biological (neuro-imaging, clinical and biochemical) data will be analysed using the Statistical Package for the Social Sciences (SPSS; v16.0), applying standard statistical thresholds (p<0.05), corrected for multiple comparisons where appropriate.

The impact of treatment on the outcomes of interest will be established using repeated measures ANOVA with time and treatment as independent variables. Individual means will be obtained for each outcome measure and group means, collapsed across the treatment arms, will be calculated to

determine treatment effects. Relationships between lifestyle, cognitive, biochemical and cardiovascular variables, and establishment of the main determinants of the response to intervention will be performed using correlation and regression analysis

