#### **Power Calculation**

For the analysis of the microbiome, we estimated the sample size based on the false discovery rate (FDR) control (Pawitan, Michiels, Koscielny, Gusnanto, & Ploner, 2005). We used the following assumptions: 50% of microbiome profiles are not associated with the case-control status and at least 80% power. Our calculation indicates that with a sample size of 30 in each experimental group, we expect to control FDR between 0.5% and 4%. FDR of 4% is considered low and hence we propose that a sample size of 30 in each group is adequate to control FDR at reasonable levels. This number is consistent with other studies investigating changes in the gut microbiome associated with diabetes (a risk factor for cognitive decline) (He, Shan, & Song, 2015) and with the only study evaluating the impact of cranberry on cognitive functions (Crews et al., 2005).

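### The protocol names two units of randomisation, the dyad and the individual, and neither the sample size nor the named tests allow for couples who share an arm

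*Protocol*

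**What the plan says.** Two statements in section 7.2 concern the unit of assignment.

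- Under Treatment to be Administered: "After screening and enrolment, each dyad will be assigned to the intervention" or to the placebo group.
- Under Assigning Subjects to Treatment Groups: "The participant will receive the treatment that has been randomly allocated to that participant number". Dyads are not mentioned there.

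Section 6 explains where dyads come from: "Married couples who live together will be particularly targeted to reduce the variability in background diet patterns". Couples are targeted but not required, and the inclusion criteria do not ask for a partner. Section 12.5 (Consent) again refers to the dyad, so the word in 7.2 is not an isolated slip.

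The analysis and sample size are written for individuals. Section 10 names "repeated measures ANOVA with time and treatment as independent variables". Microbiome Community Analysis in section 8.5 names ANOSIM/PERMANOVA between groups and time points and does not say what is permuted. The Power Calculation assumes "50% of microbiome profiles are not associated with the case-control status and at least 80% power" and concludes that, "with a sample size of 30 in each experimental group", the false discovery rate (FDR) will lie between 0.5% and 4%. No couple term, design effect, intra-couple correlation or number of couples appears anywhere.

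**The concern.** Partners who live together share a household and much of their diet, which is the protocol's own reason for recruiting them. Their outcomes are therefore likely to be positively correlated. If both also receive the same powder, that correlation adds to the variance of each arm mean. A test that counts them as two independent people understates its standard error and rejects too often. If all 60 joined as couples, there would be 30 randomised units, 15 against 15.

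What is at stake is the error rate for outcomes that a household is likely to share, such as the microbiome, metabolites and diet-related markers. The microbiome is the first objective and the only basis of the sample size. Because the two allocation statements conflict, a reader cannot tell whether the individual-level analysis will be too liberal, too conservative or about right.

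**Working it through.** **Inputs from the protocol.** 60 people, 30 per arm (section 6). Significance threshold 0.05 (section 10), taken as two-sided. Half the microbiome profiles null, power at least 80%, FDR 0.5% to 4% (Power Calculation).

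**Assumed, because the protocol gives no value.** Within-couple ICC of 0.1, 0.3 or 0.5. Share f of participants who are in couples: all (f = 1) or half (f = 0.5).

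**Step 1: the plan's own figure.** With null proportion 0.5, FDR = 0.5α / (0.5α + 0.5 × power). No effect size or per-feature α is given, so the range cannot be reproduced directly. Solving backwards at 80% power:

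- FDR 4%: α = 0.04 × 0.8 / 0.96 = 0.0333. The standardised effect that gives 80% power with 30 per arm is (2.128 + 0.842) × √(2/30) = 0.767.
- FDR 0.5%: α = 0.005 × 0.8 / 0.995 = 0.0040, and the effect is 0.960.

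The stated range therefore corresponds to effects of about 0.77 to 0.96 SD with 30 independent people per arm.

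**Step 2: partners in the same arm.** Design effect DE = 1 + f × ICC. Effective n per arm = 30/DE. True size of the unadjusted test = 2 × [1 − Φ(1.96/√DE)].

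| f | ICC | DE | Effective n per arm | True size at nominal 5% |
|---|---|---|---|---|
| 1 | 0.1 | 1.10 | 27.3 | 6.2% |
| 1 | 0.3 | 1.30 | 23.1 | 8.6% |
| 1 | 0.5 | 1.50 | 20.0 | 11.0% |
| 0.5 | 0.1 | 1.05 | 28.6 | 5.6% |
| 0.5 | 0.3 | 1.15 | 26.1 | 6.8% |
| 0.5 | 0.5 | 1.25 | 24.0 | 8.0% |

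Example: ICC 0.3, f = 1 gives 1.96/√1.30 = 1.719, and 2 × [1 − Φ(1.719)] = 0.086.

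With two time points, the time-by-treatment test is a t-test on change scores. Simulating that test with 15 couples per arm (100,000 runs) gave 6.1%, 8.7% and 11.3% at ICC 0.1, 0.3 and 0.5. A test on couple means gave 5.0% each time.

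**Step 3: the other readings.**

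- Partners always in opposite arms: replace DE by 1 − ICC (all in couples). Size is 3.9%, 1.9% and 0.6% at ICC 0.1, 0.3 and 0.5, so the test is conservative.
- Partners randomised independently of each other: simulation (40,000 runs, all in couples) gave 4.8% to 5.0% for ICC between 0.05 and 0.5, so the test is about valid.

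**Step 4: effect on the FDR statement, for illustration only.** Take the back-solved effects, all participants in same-arm couples, a valid clustered analysis and 80% power. The 0.5% to 4% range then becomes 0.9% to 5.5% (ICC 0.1), 1.9% to 8.9% (ICC 0.3) or 3.4% to 12.4% (ICC 0.5). Keeping the stated range would need 30 × DE = 33, 39 or 45 per arm.

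**The case against.** The strongest reply is that a reader might infer from the dyad sentence that this trial's p-values will be too small as a matter of fact. The documents do not support that. The subsection devoted to assignment allocates by participant number, and under that rule the individual-level test is about valid or, if couples are split, conservative. The inflation depends on which sentence is followed. This stands.

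The all-couples figures are a worst case, because couples are targeted and not required. At ICC 0.05 with half in couples, the size is only 5.3%. This also stands.

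Stable household effects drop out of change scores, so for the time-by-treatment test the relevant ICC is that of change, which may be lower than that of levels. This stands for the ANOVA. It is weaker for between-group comparisons of microbiome structure, where the ICC of levels applies. How far PERMANOVA would be inflated cannot be read from the protocol: the permutation unit is not stated, and any figure would rest on an invented structure for the UniFrac distances.

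It can also be said that a household random effect belongs in the statistical analysis plan and that this is a feasibility study. A later plan could indeed add the term. It could not settle which of two conflicting allocation rules was used, and the sample-size basis is stated in the protocol itself.

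Finally, a reader might call the diet rationale for recruiting couples simply wrong. It fails only if partners share an arm. If they are split, shared diet cancels between arms and the rationale holds.

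**Conclusion.** The point holds in conditional form. The protocol gives two units of assignment that are not reconciled, and nothing in the sample size or the named tests allows for pairing. If the dyad rule is followed, the unadjusted test is too liberal for any positive ICC. Its size at a nominal 5% runs from 5.6% (half in couples, ICC 0.1) to 11.0% (all in couples, ICC 0.5). These figures rest on assumed ICCs and couple shares and on both partners being in the same arm.

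The stated FDR range presumes 30 independent people per arm and would worsen under dyad assignment. A reader might infer that it is missed by a known amount. It is not, because without an effect size the amount cannot be fixed, and the shifted ranges above are only illustrative.

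**What to change.** Reconcile the two subsections of section 7.2 to one randomisation unit, and say what happens to participants who join without a partner.

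If the unit is the dyad or household:

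- Allocate by household, stratified by couple or single.
- In section 10, add a household random effect with small-sample degrees of freedom, or analyse household means.
- In Microbiome Community Analysis, permute whole households for between-group tests.
- In the Power Calculation, restate the FDR with the assumed couple share, ICC and effect size.
- In section 6, revise the variance rationale for recruiting couples, which no longer holds.

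If couples are split across arms by design, analyse with couple as a block and keep that rationale.

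Cost: protocol wording and one model term. Intervals widen under same-arm assignment. Standard errors rise by up to about 22% (√1.5 = 1.22) at ICC 0.5 with all in couples, and the stated precision becomes less favourable. Restating the figure needs no extra participants. Keeping the stated FDR range would need the larger arms shown in the working.
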